2.5 Blinding

PI, statistician, research assistants, care coordinators and oncology professional team members will be blinded to the randomization assignment. The UHH community or lay health workers will be unblinded to randomization assignment.

3. Outcomes, Exposures, and Additional Variables for Interest

3.1. Primary Outcome(s)

Health-related Quality of Life (HRQoL) (change in scores from baseline to 4 months post-enrollment). Health-related quality of life assessed using the 27-item Functional Assessment of Cancer Therapy – General where scores range from 0-108 with higher scores indicating better health-related quality of life.

3.2 Secondary Outcome(s) – Exploratory Outcomes Only

Health Related Quality of Life is measured by the Functional Assessment of Cancer Therapy-General: a 27-item questionnaire designed to measure four domains of HRQOL in patients with cancer. The scale is on a 5-point Likert-type scale with a score range of 0-108 with higher scores indicating greater HRQoL.

Patient Satisfaction with Decision is measured by the Satisfaction with Decision scale, a six-item scale designed to measure patient satisfaction with healthcare decision. Each item is on a 1-5 scale with higher scores indicating greater satisfaction with decision.

Patient activation is measured by the Patient Activation Measure. Each item rated on 4-point scale (1 strongly disagree to 4 strongly agree, with additional “not applicable” option. Total PAM score = [raw score]/[# items answered excepting non-applicable items] *13 ; can be transformed to a scale with a theoretical range 0–100 based on calibration tables. Raw scores can be converted into activation levels which can also be used as cut-offs:

4. Statistical Analysis Plan

We will present descriptive statistics broken out by intervention group for baseline clinical and demographic variables of interest using continuous (mean, standard deviation, median, interquartile range), and discrete (counts, percentages) where appropriate. We will also tabulate and present for each relevant covariate the percentage of subjects missing a value for that covariate, if applicable.

4.2. Primary Analysis

All patients will be included in the analysis based on their randomization assignment at time of enrollment using intent to treat. Patient data will be modeled at the participant-level.

4.2.1. Statistical Modeling

To assess our primary outcome of the effect of the intervention on change in health-related quality of life from baseline to 4-months post-enrollment between groups, we will calculate expected mean differences between groups by Generalized Estimating Equations (GEE) models where the outcome will be modeled as a function of treatment group, categorical time (baseline, 4 months, 12 months) and an interaction term between treatment group and time with an exchangeable correlation clustered within person. Significance will be assessed between groups overtime using a type III F-test on the interaction term. All ratios will be expressed as referent to the control group.

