If a patient is interested and consents verbally, he/she will be provided a welcome letter with basic information and contact phone numbers for the project. The patients will be randomized by Stanford biostatistician using a computer-generated ordered list of randomized numbers in each city. For all patients assigned to the LEAPS intervention arm, the community health worker will contact the patient to begin the intervention procedures that include assisting patients with understanding their goals of care, documenting goals of care, proactively assessing symptoms, and coordinating home-based or community-based care delivery. The intervention will be provided in addition to the usual care processes (Intervention details are provided in Appendix B).

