4.0 MATERIALS AND METHODS

After a patient is enrolled in the study, the patient will be registered and entered into the project database (CarMa) and assigned an identification number. The identification number will be used on all subject-specific documents and research-related forms.

During registration, patients will be randomized to two arms (Arm A: Usual Care or Arm B: LEAPS Intervention). Specifically, the patients will be randomized 1:1 using a simple randomization strategy in each site into two arms at each site.

All patients, throughout the study, will be asked to complete three surveys: 1) patient health-related quality of life (using Functional Assessment of Cancer Therapy – General (FACT-G) and 2) satisfaction with decision-making (Satisfaction with Decision Scale) and 3) the patient activation measure (Patient Activation Measure-13). A trained study staff member will administer the surveys at baseline (month 0) and again at 4 months and 12 months for patients in the intervention and usual care arm. Participant information will be entered into the CarMa database within 7 calendar days. Study team members will conduct electronic health record chart review of each participant and abstract date of the following: goals of care documented by oncology clinician, advance directive, and Physician Order for Life Sustaining Treatment. All health care claims data will be provided by UHH to the study team for each participant in the study at the study end which will consist of all charges and paid claims for total costs including outpatient, inpatient and pharmacy services. All study team members will be blinded to the randomization assignment. Only the community health workers will know the study assignment and the local site coordinator at each site.

As part of usual care, study PI and team members redesigned benefits such that any member of UHH with cancer will also receive waived copays if they choose to seek care at the preferred

provider in Atlantic City. We will also provide each member with access to transportation and other services to receive care at the preferred provider.

- Arm A: Usual Care (Control) / No Intervention

Patients in this arm receive “usual” care coordination from their care coordination team which includes case management by a registered nurse practitioner to address financial concerns, care navigation and coordination.

- Arm B: LEAPS/ Intervention Group

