4.2.2.1. Site-specific Modeling

We will consider refitting primary models for each site separately to explore the effect of site heterogeneity on our results.

Sample Size Considerations

The sample size of 160 participants (80 randomized to the intervention group and 80 randomized to the control group) provides greater than 90% power to detect difference in quality of life between groups (delta change =4) assuming a within-subject correlation of 0.8 and a standard deviation of the change in score equal to 9.5 based on our pilot data. The primary outcome was determined by our community partners.

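### The primary model is valid, but its 2-df interaction test does not isolate the month-4 outcome, and it leaves usable precision in baseline FACT-G unspent

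*Combined protocol and SAP*

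**What the plan says.** SAP 3.1 defines the primary outcome as FACT-G "change in scores from baseline to 4 months post-enrollment". SAP 1.1.2 places the 12-month change in FACT-G among the exploratory aims.

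For the analysis, SAP 4.2.1 states that "the outcome will be modeled as a function of treatment group, categorical time (baseline, 4 months, 12 months) and an interaction term", "with an exchangeable correlation clustered within person". The decision rule is: "Significance will be assessed between groups overtime using a type III F-test on the interaction term". Neither the protocol nor the SAP adds baseline FACT-G as a covariate or constrains the arms to a common baseline mean.

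The SAP's Sample Size Considerations claim more than 90% power for a 4-point difference with 80 per arm, "assuming a within-subject correlation of 0.8 and a standard deviation of the change in score equal to 9.5 based on our pilot data". No SD is given for any single visit.

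On timing, Protocol 3.1 moves from verbal consent to allocation without mentioning a survey: "The patients will be randomized by Stanford biostatistician using a computer-generated ordered list of randomized numbers in each city". Protocol 4.0 says "During registration, patients will be randomized to two arms", and then "A trained study staff member will administer the surveys at baseline (month 0) and again at 4 months and 12 months". Neither section says which comes first.

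**The concern.** There are two separate issues.

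**Alignment.** With three visits the arm-by-time interaction has two components, month 4 and month 12. A type III test on it asks whether the arms diverge at either time. A significant result need not mean a month-4 benefit, yet month 4 is the declared primary outcome.

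**Efficiency.** Baseline is an outcome row with its own arm effect. With complete data the month-4 coefficient is therefore the plain difference in mean change. That is unbiased, but it subtracts the whole chance imbalance at baseline, whereas the best use of baseline subtracts only the part that predicts month 4. If baseline is scored before anyone concerned knows the arm, randomisation makes the true baseline means equal, and a model that uses this can be more precise with data already collected.

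**Working it through.** **Inputs.** From the SAP sample size section: n = 80 per arm, difference 4, correlation ρ = 0.8, SD of change 9.5. From Protocol 5.1: 5% level. Assumed: two-sided test, complete data, ρ = 0.8 between all visits, month-12 SD equal to month-4 SD, and r = month-4 SD / baseline SD, which is varied.

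**Step 1. The plan's own figure.** SE = 9.5 × √(2/80) = 1.502, and 4/1.502 = 2.66. Power for the month-4 contrast (1 df) is 75.9% two-sided (84.6% one-sided), not above 90%. If 9.5 were the SD of a single score, the SD of change would be 9.5 × √(2 × 0.2) = 6.01, the SE 0.950 and power 98.8%.

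**Step 2. Free versus common baseline, month-4 contrast.** Write s₀ for the baseline SD.
- Free: variance = (2/n) × s₀² × (1 + r² − 2ρr) = (2/n) × 9.5².
- Common baseline, visit-specific variances, unstructured covariance: variance = (2/n) × s₀² × r²(1 − ρ²).
- Ratio = r²(1 − ρ²) / (1 + r² − 2ρr).

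At r = 1 the ratio is 0.36/0.40 = 0.90. At r = 0.8 it is 0.2304/0.36 = 0.64. At r = 1.25 it is 0.5625/0.5625 = 1.00, its maximum.

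| r | Variance ratio, efficient model | 1-df power | Variance ratio, exchangeable GEE with one variance |
|---|---|---|---|
| 0.8 | 0.64 | 91.4% | 0.70 |
| 0.9 | 0.79 | 85.1% | 0.80 |
| 1.0 | 0.90 | 80.2% | 0.90 |
| 1.1 | 0.97 | 77.2% | 0.98 |
| 1.2 | 1.00 | 76.0% | 1.05 |
| 1.25 | 1.00 | 75.9% | 1.08 |

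The free model has 75.9% in every row, because the SD of change is held at 9.5. At r = 1 the SE falls from 1.502 to 1.425, and the number per arm for 90% power falls from 119 to 107. On the raw-score reading of 9.5, power moves only from 98.8% to 99.3%.

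**Step 3. Covariance matters.** Adding the constraint to the planned exchangeable GEE loses precision beyond about r = 1.12; at r = 1.25 power is 72.7%. An unstructured correlation with one common scale is worse there (ratio 1.13, power 70.6%). At equal SDs, if the assumed correlations with month 12 are 0.5 and 0.6, the exchangeable ratio is 0.97 and the unstructured ratio stays at 0.90.

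**Step 4. Against the test actually planned.** At equal SDs the two free-model contrasts each have variance 2.256 (1.502²) and correlate 0.5. For effects a (month 4) and b (month 12), the 2-df noncentrality is (4/3)(a² − ab + b²)/2.256.

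| Assumed month-12 effect, with a = 4 | Noncentrality | Planned 2-df power | 2-df test, common baseline | 1-df month-4 test, free baseline | 1-df month-4 test, common baseline |
|---|---|---|---|---|---|
| 0 | 9.46 | 79.2% | 80.8% | 75.9% | 80.2% |
| 2 | 7.09 | 66.2% | 71.2% | 75.9% | 80.2% |
| 4 | 9.46 | 79.2% | 85.0% | 75.9% | 80.2% |

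The formula is symmetric in a and b. With no month-4 effect and 4 points at month 12, the planned test therefore also rejects 79.2% of the time. At r = 1.25 with a 4-point effect at both visits, the planned test has 80.8%, against 75.9% for the 1-df common-baseline test.

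**Step 5. Sensitivity.** With 10% to 30% of month-4 scores missing (assumed, equal SDs), the ratio is 0.909 to 0.928. If knowledge of the arm shifted baseline by 1 point, the common-baseline coefficient would depart from the change contrast by 1 − ρr: 0.36, 0.20 and 0.00 points at r = 0.8, 1 and 1.25.

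**Step 6. Simulation.** In 4,000 runs per case the efficient model had type I error of 4.9%, 4.8% and 4.3%, and power of 91.4%, 80.4% and 76.7%, at r = 0.8, 1 and 1.25.

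**The case against.** The strongest reply is that nothing here is an error. Outcome, model and sample size all speak of change, and the planned estimator is unbiased. That stands: a reader might infer that the primary analysis is biased or invalid, and the documents do not support that.

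The second reply is that moving from 76% to 80% is the wrong comparison, because the plan does not use a 1-df test. This also stands. At equal SDs the two changes together gain about one point over the planned test when the 12-month effect is 0 or 4. They gain 14 points when it is 2, and 9.7 of those (66.2% to 75.9%) come from the change of test. They can also reject less often than the planned test. The case for the 1-df contrast is that it answers the declared question, not that it always has more power.

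Third, the gain rests on visit SDs that the documents do not give, and on an order of events they do not fix. The blinding statements (Protocol 4.0 and 6.2, SAP 2.5) cover study team members and research assistants, which helps for the interviewer, but they do not cover the patient. Protocol 3.2 removes intervention-arm patients who withdraw consent, and Protocol 4.0 lets patients decline surveys. If baseline rows were lost unequally between arms, equal means among analysed patients would not be assured. The intention-to-treat wording of SAP 4.2 points against deletion but does not settle it. These points make the common-baseline model conditional. They do not affect the change of primary contrast.

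**Conclusion.** The point holds as an improvement in alignment and efficiency. The alignment part needs no assumption: a 2-df test over months 4 and 12 does not isolate the month-4 outcome.

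The efficiency part rests on ρ = 0.8, on baseline preceding knowledge of the arm, and on visit-specific variances. It is worth 10% of the month-4 variance at equal SDs, and between 36% and nothing over assumed SD ratios of 0.8 to 1.25. If 9.5 is really a raw-score SD, it is negligible.

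A reader might also infer that using baseline better rescues the stated power. It does not: at equal SDs the result is 80.2%, and the 91.4% at r = 0.8 depends on a ratio that the documents do not supply. The mismatch between an SD of change of 9.5 and power above 90% is a separate issue and must be resolved on its own.

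**What to change.** **1. Without condition.** In SAP 4.2.1, replace the type III sentence: the month-4 arm-by-time coefficient is the primary contrast, 1 df, two-sided 5%; month 12 is exploratory.

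**2. If timing is confirmed.** Ask the sponsor to confirm from site procedure that baseline FACT-G is scored before patient and interviewer can know the arm. A sentence in the SAP cannot make this true. If confirmed:
- Fit a longitudinal model with a common baseline mean, categorical time, and two explicit indicators, arm-at-month-4 and arm-at-month-12. Deleting the group term while keeping a full group-by-time factor only refits the free model.
- Use visit-specific variances and an unstructured within-person covariance, for example by REML. Do not add the constraint to the exchangeable GEE.
- Keep the baseline scores of all randomised patients, including those without later scores and, where consent allows, those who withdraw. Reconcile this with the removal rule in Protocol 3.2.
- Report ANCOVA of month-4 on baseline FACT-G as a sensitivity analysis, noting that it drops patients without a month-4 score.

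If timing cannot be confirmed, keep the free-baseline model with change 1.

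**Cost.** One timing check and SAP rewording before data analysis begins; no added patients or data. The second change moves the primary analysis from GEE to a likelihood model, with different missing-data assumptions. Mean parameters fall from 6 to 5 and covariance parameters rise from 2 to 6.

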3.0 STUDY ENROLLMENT AND PARTICIPANT ELIGIBILITY

3.1 Study Enrollment

Location

Health beneficiaries of UHH newly diagnosed cancer or relapsed or recurrent cancer may be referred by oncology provider clinics who partner with UHH.

Enrollment Procedures

UHH Staff assigned to the program will target potential patients on an ongoing basis using their claims data system. This includes data from a variety of sources including but not limited to Daily Inpatient Reports; referrals from hospital staff, PCPs and Specialists; referrals from other UHH staff such as those working in customer service; and referrals from Union staff and participants. The study staff will review all potential patients with newly diagnosed or recurrent disease no matter the stage or type to determine eligibility for the program. After the site PI and

study staff conduct proper screening (see below section titled “Screening Procedures” for specific details), the program will be explained to patients and patients will then be enrolled in the study.

Screening Procedures

The Site PI and staff will utilize the following claims data system documents and procedures to also screen for patients who fit the inclusion criteria listed in 3.2. Screen failures will not be included in the study data. The PI will keep a record of history and reasons for screen failures; however, any patient information gathered during this process will be destroyed.

Consent Procedures

The study staff will discuss the intervention with the patient, at the first point of contact, after eligibility has been confirmed. The study staff will introduce the program and describe the program aims and objectives. Patients will be provided adequate time to make an informed decision regarding their participation. Patients who refuse participation or have no capacity for decision-making or consent will not be included in the study.

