3.2 Participant Criteria

Inclusion criteria

1. Newly diagnosed patients with a cancer diagnosis.
2. Patients with any relapse or progressive disease (any cancer diagnosis) as identified by imaging or biopsy and confirmed by physician.
3. The patients must be 18 years or older.
4. Patients must have the ability to verbally consent and understand study procedures.

Exclusion Criteria

1. Inability to consent to the study.
2. Patients without a newly diagnosed malignancy or patients without relapse of disease.
3. Patients not eligible for fund benefits.

Criteria for Removal from Study

Any patients or families of patients in the intervention arm who withdraw consent will be removed from the study. Upon removal, usual care will be restored for these patients.

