1.1. Study Aims

1.1.1. Aim 1

The primary aim of the LEAPS program is to evaluate whether trained lay health workers who engage newly diagnosed patients with cancer and patients with newly diagnosed relapsed or progressive disease can improve Health-Related Quality of Life (HrQOL) at 4 months post-enrollment compared to baseline more than usual care.

1.1.2. Aim 2

Secondary aims which a priori defined to be exploratory include the effect of the intervention on changes in health-related quality of life from baseline to 12-months post-enrollment as compared to usual care, changes in patient satisfaction with decision-making and patient activation at 4- and 12-months post-enrollment as compared to baseline, change in emergency department and hospital use within 4- and 12-months post-enrollment, advance directive, goals of care documentation, and Physician Orders for Life Sustaining Treatment documentation at 4- and 12-months post-enrollment, and hospice and palliative care use within 4- and 12-months post-enrollment and total costs of care from baseline to death or 12-months follow-up, whichever is first. In addition, we will evaluate emergency department, hospitalization, hospice and palliative care use and total costs of care in the last 30 days of life among those who died.

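### The primary GEE is valid but leaves out disease status at entry (newly diagnosed vs relapsed or progressive); prespecifying status by time is a free, modest gain in precision.

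*Combined protocol and SAP*

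**What the plan says.** Protocol 3.2 has two routes into the trial. One is "Newly diagnosed patients with a cancer diagnosis". The other is "Patients with any relapse or progressive disease (any cancer diagnosis) as identified by imaging or biopsy and confirmed by physician". Protocol 3.1 sets no limit on stage or cancer type; screening covers "newly diagnosed or recurrent disease no matter the stage or type". SAP 1.1.1 names both groups in a single primary aim.

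Under Protocol 4.0, patients are "randomized 1:1 using a simple randomization strategy in each site", and SAP 2.4 agrees. City is the only stratum.

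For the primary analysis, SAP 4.2.1 says that "the outcome will be modeled as a function of treatment group, categorical time (baseline, 4 months, 12 months) and an interaction term" of arm with time, under an exchangeable working correlation. No baseline covariate appears in that model. Section 4 of the SAP mentions covariates only for descriptive tables and the reporting of missing values. The one heterogeneity analysis, in SAP 4.2.2.1, is an optional refit by site.

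**The concern.** A first diagnosis and a relapse or progression are different points in the course of disease. It is reasonable to ask whether quality of life over the next four months would run differently in the two groups without any intervention. If so, disease status predicts the outcome, is settled before randomisation, and is used in neither the allocation nor the model.

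What is at stake is precision. Between-group variation in 4-month change that a status-by-time term would absorb remains in the standard error of the arm contrast. There is a lesser, practical point too. If the baseline table shows the arms unequal on status, any adjustment chosen then would be post hoc.

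**Working it through.** **Inputs from the documents.** 80 per arm, target difference 4, SD of change 9.5, within-subject correlation 0.8 (SAP, Sample Size Considerations; Protocol 5.1); 5% significance level (Protocol 5.1), taken as two-sided because sidedness is not stated.

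**Assumed inputs.** Share relapsed or progressive q = 0.4. Difference between the two groups in mean 4-month change d = 2, 4, 6 or 8 points. The documents give neither figure.

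**Step 1: the plan's own power.** The SAP states more than 90%.
- Taken literally, SE = 9.5 × √(2/80) = 1.50, and power = Φ(4/1.50 − 1.96) = 75.9%. A 90% power would need 119 per arm.
- If 9.5 is instead the SD of the score, SD of change = 9.5 × √(2 × (1 − 0.8)) = 6.01 and power is 98.8%. This exceeds 90%, but it contradicts the SAP's label for the figure.

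Both readings are carried below.

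**Step 2: what status could explain (SD of change 9.5).** Variance due to status = q(1 − q)d² = 0.24d². Total variance of change = 9.5² = 90.25. Adjusted SE = √((90.25 − 0.24d²) × 2/80). Power = Φ(4/SE − 1.96).

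| d | 0.24d² | Share of variance | Adjusted SE | Power |
|---|---|---|---|---|
| none | 0 | 0% | 1.50 | 75.9% |
| 2 | 0.96 | 1.1% | 1.49 | about 76% |
| 4 | 3.84 | 4.3% | 1.47 | about 78% |
| 6 | 8.64 | 9.6% | 1.43 | about 80% |
| 8 | 15.36 | 17.0% | 1.37 | about 83% |

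The share matters little. For d from 2 to 8, adjusted power is 76.4% to 83.5% with q = 0.5 and 76.3% to 82.3% with q = 0.3.

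**Step 3: chance imbalance.** The arm difference in the share relapsed has SD √(2 × 0.24/80) = 7.7 percentage points. The chance of more than 10 points is 2 × (1 − Φ(0.10/0.077)), about 20%. The shift this puts into the estimate has SD 0.077d, which is 0.15, 0.31, 0.46 or 0.62 points. For d = 4, 0.31² = 0.096. The fall in squared SE from adjustment is 3.84 × 2/80 = 0.096. The two are the same quantity, so imbalance is not a further loss on top of Step 2.

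A 10-point imbalance would move the estimate by 0.1d, or 0.2 to 0.8 points. That is about 0.13 to 0.53 of the standard error of 1.50.

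**Step 4: the other reading of 9.5.** With SD of change 6.01, power is 98.8% before adjustment and at least 98.9% after it (q = 0.3 or 0.5).

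**Step 5: which term does the work.** The exchangeable GEE was simulated with complete data, 160 patients, d = 6, q = 0.5 and 500 runs per scenario.
- No status term: power for the 4-month contrast 77.2%, type I error 5.2%.
- Status main effect only: the same estimate to within rounding error (below 1e-13).
- Status by time: power 80.2%, type I error 6.2%. The simulation error is √(0.05 × 0.95/500), about 1 point, so 6.2% is compatible with 5%.

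A main effect shifts a patient's score equally at every visit, and the change contrast already removes that.

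These power figures are for the single 4-month contrast. The F-test in SAP 4.2.1 covers both follow-up times (2 degrees of freedom).

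**The case against.** The strongest reply is that nothing is wrong. Randomisation makes the unadjusted contrast unbiased, its standard error already includes chance imbalance in status, and leaving out a covariate contradicts nothing in the documents. That stands. A reader might infer bias or an inflated false-positive rate, but neither the design nor the simulated 5.2% supports it.

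A reader might also count imbalance as a second harm. After an adverse 10-point imbalance with d = 6 and q = 0.4, the estimate is centred on 3.4. Power is then Φ((3.4 − 1.96 × 1.50)/1.43), about 62%, against about 77% with perfect balance. An adverse imbalance at least that large occurs in about one randomisation in ten. This is the same variance component viewed after the fact, and the 76% average already includes it.

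The size also rests on assumption. No section reports FACT-G course by disease status, so a difference between the groups is plausible but not documented. At d = 2 the gain is about half a power point. The larger values of d equal or exceed the trial's whole target effect.

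A further inference would be that the sample size is too small because heterogeneity was ignored. The SAP attributes 9.5 to pilot data, which may already contain this mix, so that does not follow. The mismatch in Step 1 is a separate matter.

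Finally, SAP numbering passes over 4.1 and 4.2.2, so a covariate section could have been lost from the text available. SAP 4.2.1 nevertheless reads as a complete model specification.

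**Conclusion.** The point holds as a free improvement of low priority, not as an error. A baseline variable settled at eligibility is left out of the primary model. Using it as a status-by-time term could lower the standard error from 1.50 to between 1.49 and 1.37, and raise power from about 76% to between 76% and 83%. Those ranges assume 40% relapsed or progressive, d between 2 and 8 points, no dropout, and 9.5 as the SD of change. If 9.5 is the SD of the score, the gain is negligible.

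Nor should the status term be read as dealing with the absence of any limit on stage or cancer type. An early and an advanced first diagnosis share one category, so that variation stays unmodelled.

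**What to change.** In SAP 4.2.1, before unblinded data are seen, add disease status at entry (newly diagnosed vs relapsed or progressive, as established at eligibility) and its interaction with categorical time to the primary GEE. Include the interaction, not only the main effect. The arm-by-time terms remain the treatment effect.

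The 4-month arm difference within each group may be reported with its confidence interval, from separate fits and labelled descriptive. The SAP should say that these will be imprecise. With 40% relapsed or progressive there would be about 32 per arm in the smaller group, giving SE = 9.5 × √(2/32) = 2.4 and a 95% half-width of about 4.7 points, wider than the target of 4.

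The cost is SAP wording and three parameters (status, and status at months 4 and 12) with 160 patients. Status must be carried from screening into the analysis dataset. No extra patients, visits or assessments are needed.
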